4.5. Eligibility Criteria

4.5.1. Inclusion Criteria

Subjects who meet all the following inclusion criteria may be enrolled:

1. Able and willing to provide written informed consent.
2. Singleton pregnancy.
3. Aged 18+.
4. Greater than or equal to 22 0/7 weeks gestation.
5. Patient has none of the exclusion criteria.

4.5.2. Exclusion Criteria

Subjects who meet any of the following exclusion criteria may not be enrolled:

1. Multiple pregnancy.
2. Involvement in another clinical trial currently or previously in this pregnancy that, in the investigator's opinion, would affect the conduct of this study.
3. Medical or obstetric problem that in investigator's opinion would make the patient incapable of taking part in the study.
4. Inability to understand the consent information due to medical illness, diminished intellectual capacity, or insurmountable language barrier.

Note: Subjects may participate in more than one gestational age group during the duration of study enrollment but may only participate in each gestational age group once.

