4.3. Number of Subjects/Cases

The study includes a minimum of 30 subjects (with a maximum of 60 subjects), divided equally (10 subjects) in each gestational age group. Based on the vulnerability of subjects at the time of study eligibility, subjects may be consented prior to meeting all inclusion/exclusion criteria. Subjects must go on to meet all inclusion/exclusion criteria prior to conducting study procedures, any subject who does not go on to meet all inclusion/exclusion criteria will be considered a screen failure and will be withdrawn from the study. Subjects will be enrolled until the target numbers of 10 completed subjects in each gestational age groups are met: Group 1, 22 0/7 – 24 6/7 weeks, Group 2, 25 0/7 – 31 6/7 weeks and Group 3, \geq 32 0/7 weeks is achieved.

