10. STATISTICAL METHODS

10.1. Statistical Hypothesis

Non-inferiority of [REDACTED] with respect to Corometrics 259cx will be tested using the following primary hypothesis:

Reliability as measured by Success rate (SR) for FHR data:

$$H_0 = \text{Mean SR } [REDACTED] - \text{Mean SR (Corometrics 259cx US)} \leq -10\%$$

$$H_A = \text{Mean SR } [REDACTED] - \text{Mean SR (Corometrics 259cx US)} > -10\%$$

The test will be performed using two-sided 95% CI of the difference in Mean SR. If lower 95% CI of the difference is greater than -10%, non-inferiority will be concluded.

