10.3.1. General Statistical Methods

The study data will be presented in tables, listings, and figures. Data will be summarized using descriptive statistics. The descriptive statistics for continuous variables will include mean, standard deviation, median, Q1 and Q3, minimum, maximum, and sample size. Categorical variables will be described with counts, percentages, and sample size. A 95% confidence interval may be presented, when necessary. For comparison (between arms or against null values), categorical variables will be tested using appropriate contingency table analyses (exact or chi-square

Study Title: Maternal Fetal Device Performance Testing During Antepartum Singleton Monitoring

Study Number: SA-000072

Version Number: 2.0

Version Date: 23SEP2024

GE HealthCare

approximations), and continuous variables will be tested using Student's t-test or non-parametric methods, depending on variable distribution. P-values will be presented to three decimal places and p-values less than 0.001 will be presented as '<0.001'.

To determine whether the FHR data [REDACTED] Doppler US is non-inferior to Doppler US from the Corometrics 259cx in terms of reliability, the data collected from the two devices will be compared. Data is generated at a rate of 4 samples per second.

All the processing and statistical analysis will be done by the CSV assessed software application (CoroCare Process Software) or SAS v9.4. Using the CoroCare process software, the collected data will be stored in a CSV file which has a specific column allotted to each parameter.

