10.3.2. Analysis of Primary Endpoint(s)

Fetal Heart Rate (FHR)

For each subject, the whole length of time when both Corometrics 259cx and [REDACTED] independently record data will be considered for statistical analysis. The reliability of the FHR data will be analyzed based on the following primary endpoint.

Success rate (SR) for FHR data:

To ensure that most of the epochs are available and evaluable, the individual SR, which measures the percentage of time that [REDACTED] or Corometrics Ultrasound (independently) generates a value for FHR, will be computed per subject (irrespective of the other device generating a value or not)). Overall SR across subjects will be summarized along with its 95% CI for each device.

$$SR(FHR)_i(\%) = \frac{a_i}{a_i + b_i} * 100$$

Where,

SR_i is the ith individual SR;

a_i is represents the number of sample points when the FHR is present (i.e. has a value other than 0) for the ith subject;

b_i is the number of sample points when the FHR is not present (i.e. the device is turned on but has a value of 0) for the ith subject;

From the start of the FHR trace, only a segment of 30 minutes duration will be considered for calculating the SR value. If the data length is greater than 30 minutes, the first 30 minutes of data will be considered for analysis. If either Corometrics or [REDACTED] has less than 30 minutes of recording, the data from both devices will be eliminated from the primary endpoint analysis but could be used for engineering development. Any gaps in the data due to pausing study procedures will be excluded from the 30-minute monitoring data that will be used for analysis. The difference in mean SR (Lotus – Corometrics 259cx) will be computed along with its two-sided 95% CI to test non-inferiority. If the lower 95% CI is greater than -10%, non-inferiority will be concluded.

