10.3.4. Subgroup analysis

Analysis may also be performed for subgroups based on gestational age as an exploratory analysis.

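### One woman may contribute up to three of the 30 data sets, but the plan does not settle the unit of analysis, and its non-inferiority interval is neither stated to be paired nor adjusted for repeat women

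*Combined protocol and SAP*

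**What the plan says.** The Note in Section 4.5.2 reads "Subjects may participate in more than one gestational age group during the duration of study enrollment", limited to once per group. There are three groups, so a woman can take part up to three times.

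The count is described in different units. Section 3.2.1 refers to 30 subjects. Section 4.3 gives a minimum of 30 and a maximum of 60 subjects and adds: "Subjects will be enrolled until the target numbers of 10 completed subjects in each gestational age groups are met". Section 10.2 counts 30 Corometrics and Lotus data sets and says that the number does not come from a power calculation. Section 4.6 gives each enrolled subject one unique number.

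The decision rule in Section 10.1 is: "The test will be performed using two-sided 95% CI of the difference in Mean SR"; non-inferiority follows if the lower limit exceeds -10%. Section 10.3.2 repeats that the difference in mean success rate (SR) "will be computed along with its two-sided 95% CI to test non-inferiority". The only named methods are in 10.3.1: "continuous variables will be tested using Student's t-test or non-parametric methods, depending on variable distribution".

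SR is computed per subject and device. "From the start of the FHR trace, only a segment of 30 minutes duration will be considered for calculating the SR value". If either device's recording is short, "the data from both devices will be eliminated from the primary endpoint analysis". Gestational age enters the analysis only in 10.3.4: "Analysis may also be performed for subgroups based on gestational age as an exploratory analysis".

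**The concern.** Non-inferiority turns on one number, the lower limit of the CI. That limit depends on two things that the plan leaves open.

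The first is the unit. If subject *i* is the woman, 10.3.2 has no rule for turning two or three 30-minute traces per device into one SR, and there may be fewer than 30 units. If subject *i* is the participation, a t-interval treats one woman's visits as independent. When her device differences tend to be alike, the interval is then too narrow and the lower limit too high, which favours a non-inferiority conclusion.

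The second is pairing. Each subject is monitored on both devices (4.8, 5.1), but no sentence says that the CI is built on within-subject differences. An unpaired interval on the same data would give a different lower limit.

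The results are meant for regulatory submissions, so the interval should not be left to be chosen after the data are seen.

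**Working it through.** **Inputs from the documents.** Three groups of 10 completed subjects (4.3), and 3 × 10 = 30, which matches 10.2. Margin -10 points and a two-sided 95% CI (10.1), so the nominal one-sided error is 2.5%. Up to three participations per woman (4.5.2). Study length 4 months (Synopsis). There is no power figure to reproduce.

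**Assumed, because the documents give no value.** The intraclass correlation (ICC) of the Lotus minus Corometrics difference within a woman: 0.1, 0.3, 0.5. The number of repeat women. Any gestational-age effect on the difference. The SD of the difference.

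**Are repeats feasible?** From 24 6/7 to 32 0/7 weeks is 7 weeks 1 day, or 50 days; from 22 0/7 to 32 0/7 is 10 weeks. Four months is about 17 weeks. Two visits fit easily. Three visits each for ten women is an extreme case: every Group 1 woman must start in roughly the first 7 to 10 weeks and return twice, and nobody else enrols.

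**Variance inflation.** With *m* data sets per woman, the variance of the mean difference is multiplied by 1 + ICC × (Σm²/30 − 1).
- Five women repeat once: Σm² = 20×1 + 5×4 = 40, factor 1 + ICC/3. At ICC 0.5 this is 1.17, so the true SE is 1.08 times the independence value.
- 15 women × 2: Σm² = 60, factor 1 + ICC, or 1.1 / 1.3 / 1.5.
- 10 women × 3: Σm² = 90, factor 1 + 2×ICC, or 1.2 / 1.6 / 2.0; SE ratio 1.10 / 1.26 / 1.41.

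**One-sided error of an ordinary paired t-interval (29 df).** Simulated with the true difference at the margin, normal errors, no gestational-age effect, and 100,000 to 200,000 trials per case. Ranges show the spread between runs.

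| Design | ICC 0.1 | ICC 0.3 | ICC 0.5 |
|---|---|---|---|
| No repeats | 2.5% | 2.5% | 2.5% |
| 1 repeat woman | 2.6% | 2.6% | 2.7% |
| 2 repeat women | 2.5–2.6% | 2.7% | 2.9% |
| 5 repeat women | 2.7–2.8% | 3.0–3.1% | 3.4–3.5% |
| 15 women × 2 | 3.0–3.1% | 4.2–4.3% | 5.5–5.7% |
| 10 women × 3 | 3.6–3.7% | 6.1–6.2% | 8.5–8.6% |

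**With a gestational-age effect.** The ordinary interval counts the fixed spread between groups as noise, which offsets the clustering. With group shifts of ±0.3 SD, five repeat women give 2.3–3.2% over ICC 0.1 to 0.5. With ±0.5 SD they give 1.8–2.6%, so there is no real excess. For 10 × 3 the ranges are 3.2–7.9% and 2.5–6.9%.

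**If the CI is unpaired (58 df).** Its width relative to the paired CI is (2.002/2.045)/√(1 − r), where *r* is the assumed between-device correlation: 0.98 / 1.17 / 1.38 at r = 0 / 0.3 / 0.5. Without repeats the error is 2.5 / 1.0 / 0.3%, which is conservative when r > 0. With repeats it can go either way: for 10 × 3 at ICC 0.3 to 0.5, 6.1–8.3% at r = 0 and 1.5–2.6% at r = 0.5.

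**The proposed interval.** Let *d* be the paired difference, d̄ its mean over all 30 data sets, and G the number of distinct women. Take SE² = [G/(G − 1)] × Σ over women of (sum of her d − d̄)² / 30², with t on G − 1 df. With no repeats G = 30, and this reduces to s²/30 on 29 df, the ordinary paired t-interval. Simulated error with no gestational-age effect is 2.4–2.7% in every design in the table. With ±0.5 SD shifts and five repeat women it is 1.8–2.1%.

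**The case against.** The strongest reply is that the effect is small unless many women return. That stands: one or two repeat women leave the error at 2.9% or below, and the largest figures need every woman to repeat and a high ICC. The ICC that matters is that of the device *difference* across visits weeks apart, not of SR itself. The background section blames signal loss on movement and says that the transducer often needs adjusting; both can vary by session, so a high value is not established.

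A second reply is that 3.2.1 and 4.3 can be read as requiring 30 distinct women. That also stands as a possible reading. A reader might infer from the Note that a returning woman certainly counts again toward the 30, but the documents do not say so. The wording in 10.2 points one way and that in 3.2.1 and 4.3 the other. One subject number per woman (4.6) does not resolve it, because 10.3.2 still has no rule for several visits.

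A third reply is that pairing is implied, since both devices are used on each subject and both are dropped together. That is a fair reading, and 10.3.1 also covers tests against null values, which a t-test of differences would fit. It is not written down, however, and the same sentence covers comparisons between arms.

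Finally, the procedure steps are redacted and might deal with returning visits. The redactions in the hypothesis and primary-analysis text stand where a device name belongs, so the method for the CI is legible, and it contains no rule for repeats.

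**Conclusion.** The gap is real and its likely size is modest. The plan permits repeat participation, does not fix the unit of analysis, and does not say that the deciding CI is paired or allows for repeats. If participations are the units, women return, and device differences correlate positively within a woman, an ordinary paired CI is too narrow. The excess over 2.5% is at most about 0.4 points with one or two repeat women and about 1 point with five; error reaches 3.0–8.6% only if every woman repeats. This rests on an assumed ICC of 0.1 to 0.5 and no gestational-age effect. Without repeats, an unpaired CI would be too wide if the devices correlate positively.

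A reader might go further and infer that the planned test is anticonservative as it stands, with error near 8%. The documents do not support that. They give neither the ICC nor the number of repeats; a gestational-age effect can remove the excess when repeats are few; and an unpaired CI can err in the other direction.

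**What to change.** In 10.3.2, state that the Lotus minus Corometrics difference in SR is formed within each participation, and that the 95% CI for its mean uses a standard error clustered by woman, with t degrees of freedom equal to the number of distinct women minus 1. If nobody repeats, this is the ordinary paired t-interval, so a single rule covers every case and no mixed model is needed.

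Add a sensitivity analysis using only each woman's first participation. It drops data sets from the later gestational-age groups, so it should not be primary.

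Define *subject* consistently as woman or participation in 3.2.1, 4.3 and 10.2. Confirm in 4.6 that a returning woman keeps one subject number. Report the numbers of distinct women and of data sets.

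The cost is wording and a somewhat wider interval, with no extra subjects. With no gestational-age effect and ICC 0.1 to 0.5, the CI is about 2–8% wider with five repeat women, and 9–57% wider only if every woman repeats. For an assumed SD of the difference of 15 points, the ordinary paired half-width is 2.045 × 15/√30 = 5.6 points. At ICC 0.3 it becomes about 5.6 × 1.05 = 5.9 with five repeat women, and 2.262 × 15 × √(1.6/30) = 7.8 for 10 women × 3.

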4.6. Recruiting and Screening

Subjects will be recruited for potential enrollment in this study according to the standard procedures of the investigational site, unless otherwise specified by the Sponsor in this study protocol. All participation will be voluntary.

Following recruitment and screening, a subject will be considered enrolled (the point of enrollment) once the ICF is signed and dated. Once enrolled, the subject is assigned a unique subject number which will not contain information that could identify the subject (such as subject date of birth). Unique subject number will be used to label electronic Case report form (eCRF (MediData) data for the subject throughout her participation in the study.

Based on the vulnerability of subjects at the time of study eligibility, subjects may be consented prior to meeting all inclusion/exclusion criteria. Subjects must go on to meet all inclusion/exclusion criteria prior to conducting study procedures, any subject who does not go on to meet all inclusion/exclusion criteria will be considered a screen failure and withdrawn from the study. The number of screen failures will be included in the screening and enrollment log.

4.7. Assignment to Study Groups and Enrollment Quotas

This study is intended to be conducted at one United States site. Subjects will be divided into three groups based on gestational age groups.

Study Title: Maternal Fetal Device Performance Testing During Antepartum Singleton Monitoring

Study Number: SA-000072

Version Number: 2.0

Version Date: 23SEP2024

GE HealthCare

Table 1: Target Enrollment Groups

Subject Gestational Age Groups	Target Enrollment
Group 1: 22 0/7 – 24 6/7 Weeks	10
Group 2: 25 0/7 – 31 6/7 Weeks	10
Group 3: \geq 32 0/7 Weeks	10

4.8. Criteria for Withdrawal/Discontinuation

A subject may withdraw from study participation at any time, for any reason. The Investigator may withdraw a subject at any time, for any reason. The reasons for withdrawal and discontinuation for any subject shall be recorded on an electronic Case Report Form (eCRF). These will be reported to the Sponsor. The EC should be notified per their notification of subject withdrawal policy.

Subjects who are enrolled but do not receive/undergo the study intervention may be replaced. Withdrawn or discontinued subjects who are enrolled, and who do not complete at 30 minutes of monitoring on each device, will not be considered complete and will be replaced. Subjects who withdraw or are withdrawn by a member of the study team prior to completion of all study procedures may have their completed data used as part of the study.

5. STUDY PROCEDURES

5.1. Subject Preparation

Study staff will confirm that the subject is eligible and complies with applicable site requirements prior to starting study procedures.

After providing consent, the subject will be enrolled in the study.

Pregnant women of \geq 22 weeks gestation will undergo two 30 (+5 minute range) -minute monitoring sessions (60 minutes total).

Study Title: Maternal Fetal Device Performance Testing During Antepartum Singleton Monitoring

Study Number: SA-000072

Version Number: 2.0

Version Date: 23SEP2024

GE HealthCare

5.2. Description of Study Procedures

After the subject has provided informed consent, the subject is enrolled in the study. The study procedures are outlined below:

Study Title: Maternal Fetal Device Performance Testing During Antepartum Singleton Monitoring

Study Number: SA-000072

[figure not shown]
[figure not shown]
Version Number: 2.0

Version Date: 23SEP2024

GE HealthCare

Figure 4: Study Set-up Illustrations

5.3. Follow-up

This study does not require follow-ups. The Sponsor is responsible for assuring that the study device fulfills the biomedical safety and standards requirements of the investigational site.

No follow-up will be conducted after the subject's participation has ended. The subject will be followed for AEs from the time the research device is connected to the subject. In addition, all AEs, including those involving delayed reactions, will be followed through to resolution.

6. STUDY DATA COLLECTION AND ASSESSMENTS

Only data relevant to the conduct of the study shall be collected by the Sponsor.

Study Title: Maternal Fetal Device Performance Testing During Antepartum Singleton Monitoring

Study Number: SA-000072

Version Number: 2.0

Version Date: 23SEP2024

GE HealthCare

6.1. Primary Assessment

During the study period, the following subject information shall be collected if available:

1. Demographics to include age, race, and ethnicity.
2. Vitals to include height (cm), current weight (kg/g), calculated BMI.
3. Gestational Age (weeks, days).

During the study procedures, electronic and manual data collection shall take place. Subject data collected from the investigational system and Corometrics 259cx devices shall include:

1. Clinical outputs (digital output):
 - a. Fetal heart rate
 - b. Maternal Pulse rate
2. Plotting of the FHR and MHR on the same CTG
3. Doppler US raw data
4. FMD output
5. REM output

6.2. Secondary Assessments

During the study procedures, electronic and manual data collection shall take place. Subject data collected from [REDACTED] and Corometrics 259cx shall include:

- 1) Corometrics 259cx device parameter data
- 2) [REDACTED] device raw parameter data

6.3. Safety Assessments

The description, severity, and device relatedness of any AE or SAE during the study will be recorded. Subjects will, if necessary, be provided with emergency care. In the event of any device issues, the event will be recorded. Safety reporting will be conducted as described in this protocol.

7. QUALIFICATION AND TRAINING PLAN

7.1. Staff Qualifications

All members of the study staff participating in the conduct of the investigation shall be qualified by education, training and/or experience to perform their tasks, and this shall be documented appropriately, per ISO 14155:2020 for clinical studies. Study staff and the PI's qualification for the study will be verified by collecting their CV's and GCP certifications. If study staff or PI qualification lapses, the Sponsor will work with the site to requalify the respective role or ensure the duties are reassigned appropriately by the site. The Sponsor reserves the right to disqualify PI with appropriate justification, such as repeated issues that impact subject safety and data integrity.

Study Title: Maternal Fetal Device Performance Testing During Antepartum Singleton Monitoring

Study Number: SA-000072

Version Number: 2.0

Version Date: 23SEP2024

GE HealthCare

7.2. Training Plan for the Protocol and Research Device

Before starting the study, the study staff will be trained on the clinical investigation requirements set forth in this study protocol according to Training Plan defined by the Sponsor. This includes any individual that will operate any equipment involved in the study, collect any data that is a part of the study, analyze any data associated with the study, or is in any other way involved with the study. Training to the site personnel will be conducted prior to the first subject enrolled.

The following training information will be collected in the training log prior to study enrollment:

- Title of Training
- Training objectives
- Training logistics (who conducts training and training method)
- Target audience (who will be trained)
- Training content (including device operation, protocol review and understanding)

Study staff directly operating or maintaining the research device will be trained based on the training plan and qualified based on experience, and the hospital/clinical site policy.

The Principal Investigator will be ultimately responsible for execution of this study per the protocol and for device use in this study by members of the study staff.

8. SAFETY

8.1. Anticipated Adverse Events

Being in this study involves some foreseeable risks, which include:

The risks in this study are not expected to be beyond those of routine/similar use of comparable devices in clinical care.

Doppler Ultrasound Transducer:

The Doppler Ultrasound placement involves positioning the transducer on the volunteer subject in the same manner that is used on pregnant women in clinic or hospital settings. Possible risks associated with Doppler Ultrasound include, but are not limited to, potential skin irritation or reaction (i.e. contact dermatitis) from the transducer and/or gel. The transducer under normal operating conditions, (no fault conditions) is not expected to cause discomfort or pain, or pressure sores. Proper placement and handling or repositioning can help minimize these risks. The subject may experience positioning discomfort, and every effort will be made to ensure the subject's comfort and repositioning support. System may fail to pick up valid fetal heart rate or miss reporting of non-reactive, tachycardia or bradycardia fetal heart rate. The devices under test are not intended for clinical decision making. Subject's will be closely monitored by study staff, and testing will be discontinued if more than minor discomfort or any signs or symptoms that could indicate medically important adverse effects related to testing are observed. The risk to use of ultrasound Doppler transducers is believed to be minimal.

Abdominal Transducer Belt

The abdominal transducer belt involves positioning a belt attached to the Doppler Ultrasound Transducer around the subject's abdomen in the same manner that is used on pregnant women in clinic or hospital settings. Possible risks

Study Title: Maternal Fetal Device Performance Testing During Antepartum Singleton Monitoring

Study Number: SA-000072

Version Number: 2.0

Version Date: 23SEP2024

GE HealthCare

associated with the abdominal transducer belt include, but are not limited to, potential skin irritation or reaction (i.e., contact dermatitis), abrasions discomfort or pain, or pressure sores. The subject may experience positioning discomfort, and every effort will be made to ensure the subject's comfort and repositioning support. Subjects will be closely monitored by study staff, and testing will be discontinued if more than minor discomfort or any signs or symptoms that could indicate medically important adverse effects related to testing are observed. The risk to use of abdominal transducer belt is believed to be minimal.

Ultrasound Gel:

The Ultrasound gel is a water soluble aqueous ultrasonic gel with a pH of 6.5 to 6.95 and is used as a coupling medium to the ultrasound transducer to replace air between the patient's skin and the transducer. The Ultrasound gel is used in the same manner that is used on pregnant women in clinic or hospital settings. Possible risks associated with the ultrasound gel include, but are not limited to, potential skin irritation or reaction (i.e., contact dermatitis). Subjects will be closely monitored by study staff, and testing will be discontinued if more than minor discomfort or any signs or symptoms that could indicate medically important adverse effects related to testing are observed. The risk to use of Ultrasound gel is believed to be minimal.

Pulse Oximetry Sensor

Pulse Oximetry Sensor placement involves positioning pulse oximetry sensors on the volunteer subject in the same manner that is used on clinic or hospitalized patients. The sensors may be warm to the touch. Under normal operating conditions, (no fault conditions), the sensors are not expected to overheat. If the sensors are too warm, they will be removed immediately. If the sensors are too uncomfortable, they will be removed immediately. The risk in the use of pulse oximetry sensors is believed to be minimal.

There is always a chance of unexpected risks. Throughout the study, the Sponsor will evaluate and update safety information in study documents.

